**Epidemiology of Diabetes in Older Adults:** Approximately 25-30% of older adults in the U.S. have diabetes and another 25-30% have glucose intolerance (impaired glucose tolerance [IGT]), a pre-diabetic state (Centers for Disease Control and Prevention, 2014; Kirkman et al., 2012). The Baltimore Longitudinal Study of Aging demonstrated a progressive decline in glucose tolerance from the third through the ninth decade of life (Shimokata et al., 1991). The fasting plasma glucose increases on average 1 mg/dl per decade, and 2 hour glucose after an oral glucose load increased 5.3 mg/dl per decade. This decline in glucose tolerance was also found in data from the National Health and Nutrition Examination Survey (NHANES) III, which showed that in subjects aged 40-49 years the percentage of physician-diagnosed diabetes (fasting glucose  $\geq 126$  mg/dl) is 3.9%, whereas in subjects  $\geq 75$  years of age, prevalence increases to 13.2% (Gu et al., 1998). The percentage of subjects with undiagnosed diabetes also increases from 7.1% to 14.1% within these age groups. The cause for the high prevalence of pre-diabetes and diabetes in the aging population is not clear. However, age-dependent decreases in  $\beta$  cell function and insulin sensitivity are thought to play important roles in the deterioration of glucose homeostasis that occurs with advancing age (Donath and Shoelson, 2011). Insulin resistance in aging is thought to occur as a result of increased adiposity, sarcopenia, and decreasing physical activity (Amati et al., 2009). Insulin secretion has been shown to decline with age, at a rate of 0.7% per year in individuals with normal glucose tolerance, and this decrease in  $\beta$  cell function is accelerated approximately 2-fold in individuals with IGT (Szoke et al., 2008). Aging is also known to be associated with decreased  $\beta$  cell proliferation (Rankin and Kushner, 2009) and increased  $\beta$  cell susceptibility to apoptosis (Maedler et al., 2006). Therefore, diabetes and pre-diabetes are highly prevalent in the aging population, which increases risk for adverse aging outcomes including frailty, which ultimately leads to disability and inability to maintain independence.

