c) Frailty assessment: Individuals identified as frail (approximately 10% of the community-dwelling older adult population) ([name] and Hazuda, 2008) will be excluded. Pre-frailty is defined as the presence of 1 or 2 of: 1) self-reported unintentional weight loss of 10 lbs or more in last year, 2) self-reported exhaustion, 3) low physical activity based on the Minnesota Leisure Time Physical Activity Questionnaire, 4) weak hand grip, 5) and slowness on 10-foot walk at usual pace. These measures have been standardized in SALSA, and will be used in this study as described ([name] and Hazuda, 2008). Non-frailty is defined as the presence of 0 characteristics. Frailty will be assessed every 6 months using the Fried criteria. If a participant's frailty category or score worsens based on Fried criteria (Fried et al., 2001), it will be repeated in 3 months and then at the 6 months intervals as per the protocol thereafter. At the baseline, self-reported unintentional weight loss will be used as criteria for weight loss as stated above. However, at all subsequent visits, individuals who have lost  $\geq 5\%$  of their baseline weight will be considered to have met the criteria for weight loss. As a measure of lower extremity function, we will use the Short Physical Performance Battery (SPPB) (Guralnik et al., 1994) and the 6-Minute Walk Test (6-MWT) (Harada et al., 1999). Both the SPPB and the 6-MWT are assessments of physical function commonly used in geriatrics studies. Lower extremity strength will be measured every 6 months with a knee extension dynamometer chair. The participants will be positioned in an upright position, with the ankle to a force or torque transducer at the knee angle of  $90^\circ$ . After 3 warm-up trials, 3 trials will be conducted to measure maximal voluntary contraction force of the knee extension muscle. We will also screen for depression using the Geriatric Depression Scale (Yesavage et al., 1982) and cognitive

impairment using the Mini Mental State Examination (Folstein et al., 1975) as part of the frailty assessment.

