#### Data Analysis Plan:

### STATISTICAL METHODS & POWER CALCULATIONS

**Overview.** In all analyses for Aim 1 and Aim 2, primary inference will be drawn based on intention to treat (ITT) analyses. Average complier effect (ACE) will be used to inform the metformin effect under full compliance to treatment assignments (Angrist et al, 1996). Per protocol analyses will be used to inform the metformin effect among completers. All analyses will be carried out unadjusted and with adjustment for covariates (Table 7) and covariate interactions with treatment and time. Corrections for multiple comparisons will be applied as appropriate.

The impact of metformin treatment on the progression of frailty status (non-frail, pre-frail, frail) over time will be assessed with a repeated measures mixed effects multinomial logistic model that models the log-odds of adjacent frailty statuses in terms of an indicator of metformin use, time, and the metformin use by time interaction. The possibility of non-linear trends of the log-odds of frailty statuses will be assessed by including an additional time factor (e.g., time squared) and its interaction with metformin use. The best fitting model will be used for inference. Secondary outcomes including gait speed, 6 minute walk, SPPB, frailty index constructed from the research data collected according to the Rockwood index (Searle et al., 2008; Rockwood et al., 2007), and body composition will similarly assessed. Under the linear trend model, the beneficial impact of metformin will be revealed by a significant time by treatment interaction associated with the log-odds of frailty status progression, indicating that the rate of increase in the likelihood of frailty progression over time is reduced in the metformin arm relative to the placebo arm. Under the non-linear trend model, the impact of metformin will be revealed by a significant reduction in the log-odds of frailty status progression in the metformin arm versus placebo at certain time points during the follow-up. SAS proc **nlmixed** will be used in the mixed effects model analyses. Proc **nlmixed** is preferred over other mixed effects modeling procedures such as GEE because it is valid under missing at random (MAR) assumption, accommodates linear and non-linear modelling, and uses maximum likelihood estimation.

Table 7. Covariates included in statistical analyses

Categories of covariates	Baseline	Time Varying
Demographics (age, sex)	X	
BMI (obesity), sarcopenia	X	X

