Lipids, blood pressure	X	X
Fasting glucose, HbA1c, Insulin Sensitivity from OGTT (Matsuda) and Insulin Clamp	X	X
Inflammation (systemic & muscle), Insulin Signaling (muscle)	X	X
Diabetes conversion		X
Pioglitazone use		X

Of secondary interest, a per protocol analysis will be carried out with restriction to patients who follow the protocol throughout the study, and where those who drop out, violate the protocol or change treatments are excluded. Separately, those who change treatments will be summarized and described. To account for any treatment change, we will also consider principal stratification analysis (which requires categorization of patients based on treatment change patterns) and marginal structural modeling (which obtains the overall metformin effect accounting for treatment change, and time-varying covariates (e.g., diabetes status), and outcomes (e.g. frailty, physical function) history.

Metformin dose will be handled in the statistical analysis by conducting dose-response analysis among metformin users. Several options of metformin dose/exposure variables will be considered in separate analyses: average daily dose, clinical meaningful threshold for average daily dose, total days of supply, and clinical meaningful threshold for total days of supply. Should there be any discrepancy among these dose-response analyses, we will reconcile these results for the final interpretation.

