**3.D.4. Aim 2.** To address the question as to whether an anti-frailty effect of metformin is mediated by its insulin sensitizing and anti-inflammation effects, we will employ the unified mediation analysis framework by Vanderweele. Insulin sensitivity (Matsuda index derived from the OGTT) will be measured at baseline, 6, 12, 18 and 24 months, and 8 biomarkers of systemic inflammation (IL-6, CRP, TNFa, IL-1RA, TNFs R1 and 2, fibrinogen, and transferrin), insulin sensitivity (clamp) and multiple biomarkers of muscle inflammation and insulin signaling (NF $\kappa$ B and MAPK signaling, and mRNA levels of inflammatory cytokines) will be measured at baseline, 12 months, and 24 months. First, we will conduct separate repeated measures mixed effects linear model analyses to assess the effect of metformin treatment on each insulin sensitivity and inflammation measure. In each of these analyses, the outcome (or its normal transformation) will be modelled in terms of an indicator of metformin treatment, time, the treatment by time interaction, and covariates. The coefficient associated with the treatment by time interaction will inform the effect of metformin on the temporal change of each biomarker. We will then conduct repeated measures mixed effects multinomial logistic model to assess whether the odds of an increase in the frailty score is associated with the change in insulin sensitivity from baseline to 24 months ( $\Delta$ IS), and change in inflammation from baseline to 24 months ( $\Delta$ I) by modelling the log-odds of frailty worsening in terms of metformin treatment, time,  $\Delta$ IS,  $\Delta$ I, (metformin) treatment $\times$ time, and covariates. The treatment $\times$ time $\times$  $\Delta$ IS and treatment $\times$ time $\times$  $\Delta$ I interactions will be explored to assess whether metformin attenuates the effect of  $\Delta$ IS and  $\Delta$ I: this effect will be revealed by a significant coefficient associated with treatment $\times$ time $\times$  $\Delta$ IS or treatment $\times$ time $\times$  $\Delta$ I. If some  $\Delta$ IS and  $\Delta$ I measures are collinear, then we will model the odds of frailty worsening in terms of  $\Delta$ IS and  $\Delta$ I separately. All of these analyses will be initially carried out for a pair of an inflammation biomarker and an insulin sensitivity marker separately. Aim 2 will be verified in principle if (i) metformin is associated with significant increase in  $\Delta$ IS and decrease in  $\Delta$ I; and (ii) frailty worsening is

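### Aim 2 tests change in insulin sensitivity against a frailty score that counts low activity, with no activity measure among its covariates, so that association is open to confounding and overlap

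*Combined protocol and SAP*

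**What the plan says.** Aim 2 asks whether any anti-frailty effect of metformin runs through insulin sensitivity and inflammation. Section 3.D.4 states that "we will employ the unified mediation analysis framework by Vanderweele". It models worsening of the frailty score on treatment, time, change in insulin sensitivity (ΔIS), change in inflammation (ΔI), treatment by time, and covariates. The stated purpose is "to assess whether the odds of an increase in the frailty score is associated with the change in insulin sensitivity from baseline to 24 months"; inflammation is handled in the same way. Aim 2 counts as verified in principle if three criteria hold:

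- (i) metformin raises ΔIS and lowers ΔI;
- (ii) worsening goes with lower ΔIS and higher ΔI;
- (iii) the indirect effects are significant.

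The statistical overview fixes the adjustment set: "All analyses will be carried out unadjusted and with adjustment for covariates (Table 7) and covariate interactions with treatment and time". The table is titled "Table 7. Covariates included in statistical analyses". Its rows are age and sex; "BMI (obesity), sarcopenia"; lipids and blood pressure; "Fasting glucose, HbA1c, Insulin Sensitivity from OGTT (Matsuda) and Insulin Clamp"; inflammation and insulin signaling; diabetes conversion; and pioglitazone use. Activity is not listed.

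Activity appears in three other places:

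- **Background (Epidemiology of Diabetes in Older Adults):** "Insulin resistance in aging is thought to occur as a result of increased adiposity, sarcopenia, and decreasing physical activity".
- **Frailty assessment (Screening Tests, item c):** one of the five items is "low physical activity based on the Minnesota Leisure Time Physical Activity Questionnaire".
- **Study Procedures, item a, and the visit schedule:** a wrist activity monitor is worn over 10 days, before randomisation and at two later time points (visits 2, 9 and 15). The analysis plan assigns these data to no model.

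**The concern.** Randomisation protects the effect of metformin on ΔIS. It does not protect the association between ΔIS and frailty, which is observational within the trial. A participant who becomes less active may lose insulin sensitivity and, by definition, may also gain a frailty point. The two would then move together even if insulin sensitivity had no effect on frailty.

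The background names three contributors to insulin resistance: adiposity, sarcopenia and activity. Table 7 covers the first two and omits the third, although the trial measures it in two ways. Section 3.D.4 names no mediator-outcome confounders, no sensitivity analysis for unmeasured confounding, and no version of the score without the activity item. The marginal structural model in the statistical overview deals with treatment change, not with mediation. At stake is whether a reported insulin-sensitivity mechanism can be told apart from inactivity counted on both sides of the model.

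**Working it through.** **No plan figure to reproduce.** The plan states no power or error rate for the mediation test. The simulation takes these inputs from the documents: 60 completers per arm (120 in total), a significance level of 5%, and 47–58% worsening in frailty (0.47 × 120 = 56.4 and 0.58 × 120 = 69.6, matching the plan's 56–70). It uses 52% worsening.

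**Assumptions not in the documents.** These are the correlation r between activity change and ΔIS, and the share p of participants who gain the activity item. No item-level rate is given. If 52% worsening came from five independent, equally likely items, each would be gained by 1 − 0.48^(1/5) = 0.137, or about 14%. A share of 25% is taken as a higher value.

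**Set-up.** Activity change U is standard normal and untouched by treatment. ΔIS = a × arm + r × U + √(1 − r²) × noise, where a is the metformin effect in SD units. The activity item is gained when U falls in its lowest fraction p. The other items are gained independently with probability 1 − 0.48/(1 − p), which is 0.44 for p = 14% and 0.36 for p = 25%, so total worsening stays at 52%. ΔIS has no effect on frailty. Worsening (yes or no) is regressed by logistic model on arm and ΔIS, with about 2,000 trials per setting.

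**Result 1: false ΔIS association, two-sided 5%.**

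| r | p = 14% | p = 25% |
|---|---|---|
| 0.2 | 7% | 14% |
| 0.3 | 12% | 25% |
| 0.5 | 27% | 61% |

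Repeat runs put the last cell between 57% and 64%. At p = 10%, the rates for r = 0.2, 0.3, 0.4 and 0.5 are 6%, 8%, 12% and 18%. With r = 0, with U in the model, or with the activity item removed, the rate is about 5%.

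**Result 2: partial proxies.** At p = 25%, adding a covariate correlated 0.5 with activity change (assumed, standing in for BMI and sarcopenia) leaves 12%, 18%, 29% and 45% for r = 0.2, 0.3, 0.4 and 0.5.

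**Result 3: criteria (i) and (ii) together, both markers in one model.** With p = 25% and assumed metformin effects of 0.5 SD on ΔIS and on ΔI:

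- activity does not drive ΔI: 0.5% (r = 0.3) and 1% (r = 0.5);
- activity also drives ΔI: 3% (both correlations 0.3), 4% (0.5 and 0.3) and 8% (both 0.5).

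Allowing for simulation error, the range is about 0–9% per marker pair, before criterion (iii). The ceiling depends on the 0.5 SD assumption. At 0.5 SD, metformin's effect on one marker is significant in about 78% of trials, so on both in about 0.78² = 61%. At 0.8 SD it is significant in about 99%. The worst case would then be roughly 0.08/0.61 = 13%.

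**Result 4: limits of dropping the item.** If activity also correlates 0.3 with the other frailty items, the four-item model at p = 25% still rejects in 12% (r = 0.3) to 25% (r = 0.5) of trials.

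**The case against.** Five points can be made for the plan.

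- **The decision rule is wider than one coefficient.** Aim 2 needs ΔIS and ΔI to pass together. This stands. A reader might infer from the 7–61% range that Aim 2 would wrongly claim a mechanism that often. The documents do not support this: the planned rule requires inflammation as well, and they cite no link from activity to inflammation. A false insulin-sensitivity component can still be reported.
- **BMI and sarcopenia, baseline and time-varying, absorb part of the effect.** This stands in part. They shrink the bias but do not replace activity (Result 2). The rates in Result 1 describe a model without Table 7.
- **The plan does not say inactivity causes insulin resistance.** This stands. The background says it is thought to contribute, and it speaks of ageing in general, not of change over 24 months in this trial.
- **Adjusting can do harm.** This stands. The background links insulin resistance to weaker quadriceps and slower gait, so inactivity could lie on the pathway from insulin resistance to frailty. Adjusting for activity change, or deleting the item, could then remove part of a real effect. It is also tempting to treat the four-item score as a cure or as a condition for claiming mediation; Result 4 shows why it cannot be either.
- **This is a pilot, and Aim 2 is to be verified only in principle.** True, but the remedy needs only data already collected.

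**Conclusion.** The gap is real and can be read directly from the text. Activity is part of the outcome, is a suspected contributor to the mediator, and is in no Aim 2 model. The ΔIS-frailty association in criterion (ii) and the ΔIS part of the indirect effect in criterion (iii) are exposed. Criterion (i) and Aim 1's randomised comparison are not.

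The size cannot be fixed from the documents. A false ΔIS association in about 7–61% of trials rests on assumed correlations of 0.2–0.5, an assumed 14–25% gaining the activity item, and a single binary endpoint in place of the planned repeated-measures multinomial model. At the lower end the excess over 5% is small. For criteria (i) and (ii) together the risk is about 0–9% per marker pair at 0.5 SD metformin effects. It is about 1% or less unless activity also drives inflammation. Testing many marker pairs would raise the chance of at least one false result, but that is a separate multiplicity question.

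**What to change.** 1. Add baseline activity, from both the monitor and the questionnaire, to the Aim 2 covariates. This is safe, but it does not block confounding by change in activity.
2. Prespecify the Aim 2 frailty models with the low-activity item removed (0–4 score), as a sensitivity analysis and not as a gate.
3. Prespecify a second sensitivity analysis that adds monitor-measured activity change to the mediator-outcome model.
4. State in the plan that the second analysis may over-adjust if activity lies on the pathway, and that neither removes the confounding fully if activity also drives the other frailty items.
5. Describe an insulin-sensitivity mechanism as supported only with these results shown beside the main one.

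The cost is extra model runs on existing data. The four-item score is coarser and may drop part of a real effect.

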**Role of Inflammation in Diabetes:** Type 2 diabetes is known to be an inflammatory condition, associated with increased IL-6 and tumor necrosis factor (TNF) - $\alpha$  in plasma (Pickup, 2004) and enhanced activity of the transcription factor nuclear factor (NF) $\kappa$ B, a master regulator of inflammatory responses (Tantiwong et al., 2010). Pre-diabetes also is associated with increased inflammation and the presence of inflammation in the pre-diabetic state predicts the onset of diabetes (Haffner, 2003; Pradhan et al., 2001). The mechanism linking impaired insulin secretion and function of type 2 diabetes with inflammation is thought to be a result of excess glucose and free fatty acid induced stress to insulin-sensitive tissues, particularly adipose and liver, leading to local production of inflammatory cytokines such as TNF $\alpha$ , IL-1  $\beta$ , and CC-chemokine (CCC) ligand 2, CCC 3, and CCC 8 (Donath and Shoelson, 2011). The local release of cytokines promotes inflammation in other tissues, including the pancreatic islet cells (Donath and Shoelson, 2011). Concentrations of circulating IL-6 and CRP (the hepatic expression of which is triggered by IL-6) are known to be increased in obesity and predict the incidence of type 2 diabetes (Pradhan et al., 2001). Therefore, inflammation plays a major role in the pathogenesis of type 2 diabetes.

Although a general consensus has emerged that inflammation plays a role in the etiology of frailty, the molecular basis for the increased inflammation that leads to frailty is unknown. Because diabetes is a major predictor of frailty based on our own work ([name] et al., 2012) and that of others (Kalyani et al., 2012; Woods et al., 2005), we hypothesize that the inflammation observed in insulin resistance and hyperglycemia are in part responsible for the inflammation observed in frailty.

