
associated with significant decrease in  $\Delta IS$  and increase in  $\Delta I$ ; and (iii) the indirect effects of metformin (mediated by  $\Delta I$  and  $\Delta IS$ ) calculated based on Vanderweele are significant.

**3.D.5. Power Calculation for Aim 2. Inflammation.** A 3 month clinical trial of insulin sensitizers versus placebo in patients with impaired glucose fasting glucose or diabetes found decreased TNF $\alpha$  in treated patients (effect size =1.5) . Assuming the same or larger decrease in TNF $\alpha$ , 60 completers in each group, 6 repeated measures, autocorrelation 0.5, and overall type 1 error of 0.05, we expect to have power  $\geq 95\%$  to detect a group difference with regard to mean TNF $\alpha$  and power  $\geq 95\%$  power to detect an increase in TNF $\alpha$  and frailty worsening in the combined cohort [PASS Version 11, NCSS Kaysville UT 2011]. **Insulin sensitivity.** The Diabetes Prevention Program demonstrated improved fasting glucose in metformin treated adults (decrease of 4.1 mg/dL) with pre-diabetes and increased fasting glucose (by 0.4 mg/dL) in placebo group . Assuming the same treatment effect on fasting glucose in this study, and n=60 completers per arm, this study will attain a power of 80% for testing the null hypotheses of no treatment effect, two sided testing, 6 repeated measures, and an autocorrelation of 0.5 [PASS Version 11, NCSS Kaysville UT 2011].

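### When insulin-sensitivity and inflammation changes are collinear, Aim 2 falls back on separate frailty models, and nothing stops those results from verifying two mechanisms when only one acts

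*Combined protocol and SAP*

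**What the plan says.** Section 3.D.4 sets out the mediation analysis for Aim 2. For the method, "we will employ the unified mediation analysis framework by Vanderweele". Whether the mediators are taken singly or jointly is not specified.

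The default frailty model contains treatment, time, ΔIS, ΔI, treatment by time, and covariates, so each mediator is adjusted for the other. The unit of analysis is a pair: "All of these analyses will be initially carried out for a pair of an inflammation biomarker and an insulin sensitivity marker separately".

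The fallback is one sentence. If some of the "measures are collinear, then we will model the odds of frailty worsening in terms of" ΔIS and ΔI separately. No threshold for collinearity is given.

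The decision rule follows directly: "Aim 2 will be verified in principle if (i) metformin is associated with significant increase in" ΔIS and decrease in ΔI. Criterion (ii) requires frailty worsening to be associated with both changes. Criterion (iii) requires that "the indirect effects of metformin (mediated by" ΔI and ΔIS) be significant. The rule does not say that either association or indirect effect must hold given the other mediator. It does not exclude results from the separate models, and it defines no joint indirect effect.

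**The concern.** Aim 2 names two potential mechanisms, and its rule concludes that both operate. The fallback removes mutual adjustment in the situation where removing it does most harm. With one mediator left out, the other picks up part of the omitted effect, and the closer the correlation, the larger that part. If metformin shifts both, as criterion (i) expects, the omitted mediator affects frailty, is related to the retained mediator, and is itself changed by treatment.

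Correlation between the two is plausible on the plan's own account. The background section on inflammation in diabetes ends: "Therefore, inflammation plays a major role in the pathogenesis of type 2 diabetes". The same section also describes glucose and fatty-acid stress producing inflammatory cytokines, so it supports links in both directions.

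At stake is the mechanistic conclusion: two pathways could be declared on evidence for one. The problem is symmetric, because an inactive insulin-sensitivity pathway could pass in the same way.

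**Working it through.** **The plan's own figures (section 3.D.5).** The inputs are "60 completers in each group, 6 repeated measures, autocorrelation 0.5, and overall type 1 error of 0.05", with an effect size of 1.5 on TNFα. A single measure already gives a noncentrality of 1.5 × √(60/2) = 8.2 and power above 0.999, consistent with the stated 95% or more. The 80% for fasting glucose cannot be checked because no SD is given. A difference of 4.1 + 0.4 = 4.5 mg/dL at 80% power with one measure implies an SD of 4.5 / (2.80 × √(2/60)) ≈ 8.8, which is a shift of about 0.5 SD. Neither figure covers mediation.

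**Size of the misattribution.** Let r be the within-arm correlation of ΔIS with the fall in inflammation. If only ΔIS acts, the coefficient in the separate ΔI model is roughly r × the ΔIS effect. At r = 0.9 and 0.8 log-odds per SD this is 0.72, and the simulated median was also 0.72.

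**Is the fallback triggered?** Variance inflation is 1/(1 − r²), which gives 1.3, 2.0, 3.6, 5.3 and 10.3 at r = 0.5, 0.7, 0.85, 0.9 and 0.95. Correlations of 0.5-0.7 would rarely be called collinear, so the results below use 0.85 and 0.9.

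**Simulation set-up.**
- 60 per arm, with frailty reduced to a binary worsening outcome.
- ΔI has no effect on frailty and there is no direct treatment effect.
- For settings A and B the intercept is 0.32, since ln(0.58/0.42) = 0.32. The 58% is the upper end of the plan's projected worsening rate (47-58%).
- The correlations, the mediator effects on frailty and the metformin shifts are assumptions, except the 1.5 SD shift in ΔI, which is the plan's TNFα figure.
- A and B used 2,000 trials per setting, with Monte Carlo error of about 1 percentage point; C and D used 1,500-4,000.
- The plan names no test for criterion (iii), so two are shown: joint significance of the two links, and product of coefficients with a delta-method standard error.

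| Setting: ΔIS log-odds per SD; shift in ΔIS; shift in ΔI | r | False ΔI association, separate model | Full rule, joint significance | Full rule, delta method | False ΔI association, both in model |
|---|---|---|---|---|---|
| A: 0.66; 0.6; 0.6 | 0.85 | 81% | 68% | 46% | 4% |
| A | 0.9 | 85% | 74% | 52% | 4% |
| B: 0.66; 0.6; 1.5 | 0.85 | 80% | 71% | 57% | 6% |
| B | 0.9 | 85% | 75% | 60% | 5% |
| C: 0.8; 0.5; 1.5 | 0.9 | 95% | not run | 59% | 2% |
| D: 0.8; 0.5; 0.5 | 0.9 | 95% | not run | 48% | 3% |

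C and D count only associations in the stated direction, so their nominal rate is 2.5%.

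**Checks.**
- At r = 0 the separate model in A gives 5%, so the excess comes from the omitted correlated mediator.
- If metformin does not lower ΔI, criterion (i) blocks the false inflammatory pathway (below 1% in setting D with the ΔI shift set to zero).
- Keeping both mediators costs power. In A, the true ΔIS pathway (joint significance) is found in 83% of trials at r = 0, 37% at 0.85 and 27% at 0.9.

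**Reversed order.** Now let metformin lower inflammation by 0.6 SD, let inflammation drive ΔIS with correlation r, and let ΔIS act on frailty (0.66 log-odds per SD). The separate ΔI model is significant in 81% of trials at r = 0.85 and 85% at 0.9; with both in the model the rate is 5%. These are the same rates as in A, but here the separate-model result is a correct detection of an upstream effect. The data alone do not distinguish the two cases.

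**The case against.** The strongest reply is causal order. A reader might infer that a significant ΔI effect from the separate model is always spurious, and that only the joint model should support a pathway claim. The documents do not support that. If inflammation lies upstream of insulin resistance, the inflammatory pathway exists, and a joint-model-only rule would suppress it by conditioning on the downstream mediator. This stands, and it limits both the claim and the remedy.

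The reply that the default is already the joint model also stands: the separate models apply only under collinearity, so error rates at correlations of 0.5-0.7 should not be held against the plan.

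Third, the fallback is written for the association model behind criterion (ii), and the text does not say that criterion (iii) uses the separate models. That is right; the defect is that it does not rule this out either, and naming a mediation framework does not settle it.

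Fourth, Table 7 lists both insulin sensitivity and inflammation as covariates, so an adjusted separate model might bring the other mediator back. But the overview asks for every analysis unadjusted and adjusted and does not say which decides verification. If adjustment did restore the other mediator, the fallback would undo itself. This ambiguity is no safeguard. Nor is the general promise of multiplicity correction, which does not remove bias.

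Finally, this is a pilot, and the two-mechanism rule is conjunctive, which lowers the false-pass rate below that of a single pathway. Both are fair, and the full-rule rates above already reflect the second.

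**Conclusion.** The concern holds in a limited form. Under strong collinearity, with metformin moving both mediators, the fallback together with the verification rule can declare two mechanisms when only one acts. Under the assumed effects, at correlations of 0.85-0.9, false ΔI associations occur in about 80-95% of trials, against about 5% with both mediators in the model. False full verification is about 70% by joint significance and about 46-60% by the delta method, if criterion (iii) is taken from the separate models.

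The percentages rest on assumed correlations and effects and on a simplified outcome; the documents give no correlation between the mediators. The direction of the error does not depend on those values, but calling it an error does depend on inflammation not acting upstream of insulin sensitivity. A reader might take the background section to fix that order. It does not, since it describes links both ways.

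**What to change.** In section 3.D.4:

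1. State the threshold at which a pair counts as collinear, and the assumed causal order of ΔI and ΔIS.
2. Above the threshold, base criteria (ii) and (iii) on one joint indirect effect through ΔIS and ΔI together, and state that the split between them is not estimable. Treating the pair as a set does not require knowing which mediator comes first.
3. Keep the separate models as descriptive only, and do not count them as verifying a specific pathway.
4. Say whether the Table 7 adjustment includes the other mediator, and which version decides verification.

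This is SAP wording only; no data collection or sample size changes. The downside is that with highly correlated mediators the trial can claim only a combined pathway. The power figures above suggest that this is about what 120 completers can support.
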